9.3.1.2 Clinical Laboratory Results

The clinical laboratory results (continuous parameters) will be presented by summary statistics for each laboratory parameter within the specific test panel. In addition, summaries will include the change from baseline values at each scheduled post-baseline visit. Laboratory values will be compared to normal range of the laboratory and values that fall outside of the normal ranges will be flagged as: H (High) and L (Low) in the data listings.

9.3.1.3 Vital Signs

All vital signs parameters will be summarized using descriptive statistics for each treatment group for all timepoints assessed, including change from baseline for all post-treatment assessments.

9.3.1.4 BCVA

BCVA will be summarized using descriptive statistics for each treatment group for all time points assessed, including change from baseline for all post-treatment assessments. BCVA assessment will be split between the study eye and fellow eye.

9.3.1.5 Ophthalmic Imaging

Ophthalmic imaging will be conducted at the last study visit (exit/early termination), and these results will be measures of interest. Parameters will be summarized using descriptive statistics by treatment group. Ophthalmic Imaging assessments will be split between the study eye and fellow eye.

9.3.1.6 Intraocular Pressure

IOP will be summarized using descriptive statistics for each treatment group for all time points assessed, including change from baseline for all post-treatment assessments. BCVA assessment will be split between the study eye and fellow eye.

9.3.1.7 Systemic PK

The amount of study drug present in the patient plasma will be summarized at each time point. ONL1204 concentrations that are below the quantitation limit (BQL) will be set to 0 if before the first quantifiable concentration and to 0 thereafter for all descriptive analyses of ONL1204. For the calculation of geometric mean and geometric CV%, all BQL values will be set to missing. The number of BQL values at each time point will be summarized through frequency counts and percentages.

9.3.1.8 Other Parameters

Other safety data will be listed by treatment group and may be further evaluated through descriptive summaries. Concomitant medications will be coded using the World Health Organization drug dictionary and summarized by treatment group.

9.3.2 Ocular PK Analyses

Ocular PK will be analyzed per treatment group as well as per protocol across all treatment groups. Concentration data from the bioanalysis of the ocular fluid samples will be reported in summary tables. Pharmacokinetic parameters (e.g., Tmax, Cmax, terminal t1/2, AUC0-last, and AUC0-infinity) may be calculated based on the concentration data from the bioanalysis of the collected samples, if appropriate.

9.3.3 PD Analyses

Pharmacodynamic statistical analyses will be conducted based on the proteomic analysis of cytokine biomarkers in ocular fluids.

Vitreous and aqueous humor sample results and changes from baseline will be summarized by treatment group. Treatment effect will be assessed within and between treatment groups using an appropriate statistical method. The analysis will be based on log-transformed data if required.

Measurements below or above the limits of detection will be censored at the laboratory reported lower or upper limit of detection. Analytes will not be included in the analyses if more than half of the measurements in a treatment group are below the limit of detection.

Further exploratory analyses may be performed to evaluate potential dose-related measures.

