16 patients will be enrolled and treated, starting with the lowest dose, Cohort 1. The first patient in each cohort will be observed for at least 14 days post surgery (through Visit 5) before the rest of the cohort can be enrolled. The safety review committee will review the data prior to clearing the sentinel patient and enrolling the remainder of the cohort. After all 4 patients in a cohort have completed Visit 5, the safety review committee will review available safety data to determine if dose limiting toxicity exists that prohibits enrolling the next higher dose cohort. The respective IRB's will be informed of the outcome of the SRC meetings.

If there are no safety concerns, the next cohort will start treatment.

*Patients may be replaced who do not receive an injection of study medication, or for discontinuing from the study for reasons unrelated to treatment before completing Visit 4.

Page 8 of 52

TABLE OF CONTENTS

CLINICAL RESEARCH PROTOCOL						
Clinical Protocol Approval Form2						
Confidentiality and Investigator Statement						
Study Summary	4					
TABLE OF CONTENTS	8					
Table of Tables	.10					
Table of Figures	.10					
LIST OF ABBREVIATIONS	.11					
1 INTRODUCTION AND RATIONALE	.14					
1.1 Background	.14					
1.2 ONL1204	.14					
1.2.1 Preclinical Experience	.14					
1.2.2 Clinical Experience	.16					
1.3 Study Rationale	.16					
1.3.1 Rationale for the Proposed Doses	.16					
1.3.2 Rationale for Pharmacokinetic testing	.17					
1.3.3 Rationale for Vitreous Tap and Pharmacodynamic Analysis	.17					
1.4 Potential Risks and Benefits	.18					
1.4.1 Potential Risks of Study Product	.18					
1.4.2 Potential Risk to Fetal Development	.18					

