1.3.3 Rationale for Vitreous Tap and Pharmacodynamic Analysis

A vitreous tap will be performed at the time of diagnosis/IVT injection of drug, and an undiluted vitreous sample as well as aqueous sample will be taken at time of surgery. This will allow for assessment of the cytokine profile before and several days after administration of ONL1204. This will allow for the potential identification of a biomarker for proof of principle of target engagement, via analysis of cytokines and other potential molecular biomarkers that impact visual acuity after surgical repair of retinal detachment. The described procedures are routine for retinal surgeons, with the risk of endophthalmitis thought to be similar to that of IVT injections (1 in 2000-3000 patients).

Page 18 of 52

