4.1 Overview of Study Design

Sixteen patients will be enrolled in 4 ascending dose groups.

After signing informed consent and meeting all eligibility criteria, patients will undergo a vitreous tap for cytokine and other potential molecular biomarker analysis followed by a single intravitreal injection of ONL1204. This will occur on the day of diagnosis (Day 1). Safety visits will be conducted 1 day post-injection and per Investigator's discretion until Visit 3. At Visit 3 (3+ days post-injection, in accordance with standard of care) patients will undergo surgical repair of their retinal detachment with vitrectomy (with or without scleral buckling) and gas or oil tamponade. At the time of surgery, an undiluted vitreous sample will be collected for pharmacokinetic and pharmacodynamics analyses, and an aqueous sample will be collected for pharmacodynamic analysis. Additional safety visits will be conducted 1 day post-surgery, 14 (+4 days) days post-surgery, Weeks 6, 9 (\pm 7 days each), and Week 24 (\pm 14 days; study exit).

As this is a first-in-human safety study of ONL1204, the first patient in the first cohort will receive the lowest dose of ONL1204. After this patient completes Visit 5 (14 +4 days post-surgery) and a safety review committee reviews the data, the remainder of the patients in that cohort will be enrolled. After all patients in the cohort have completed Visit 5, the SRC will review the available safety data to determine if dose

limiting toxicity exists that prohibits enrolling the next higher dose cohort. This process will be repeated until escalating to the top dose.

The following doses will be evaluated: $25 \ \mu g$, $50 \ \mu g$, $100 \ \mu g$, and $200 \ \mu g$ ONL1204. ONL1204 is available in vials with concentrations of 0.5 mg/mL and 2 mg/mL. Therefore, a volume of 0.05 or 0.1 mL will be injected into the study eye.

Patient participation will be approximately 24 weeks (6 months): a single injection treatment and 24 weeks of follow-up.

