9.1.2 Sample Size

The number of patients to be enrolled has been selected to provide information for this Phase 1 study. No formal sample size calculation is provided given the pilot nature of this study.

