11. PHARMACODYNAMICS

Pharmacodynamic statistical analyses will be conducted based on the proteomic analysis of cytokine biomarkers in ocular fluids.

The following PD endpoints will be assessed:

- Vitreous Humor sample collected at pre-injection baseline by vitreous tap
- Vitreous Humor sample from the undiluted sample collected at the time of surgery
- Aqueous Humor sample collected at the time of surgery

Analyte concentrations will be provided for the vitreous humor and aqueous humor samples.

All PD endpoints will be analyzed separately by ONL Therapeutics.

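### The protocol's cytokine exclusion rule counts post-dose samples, so on some readings it can remove an analyte because the drug lowered it below the detection limit

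*Protocol*

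**What the plan says.** Protocol 9.3.3 (PD Analyses) plans summaries of vitreous and aqueous results, and of changes from baseline, by treatment group. It adds: "Treatment effect will be assessed within and between treatment groups using an appropriate statistical method". On detection limits it makes two statements. The first covers individual values: "Measurements below or above the limits of detection will be censored at the laboratory reported lower or upper limit of detection". The second covers whole analytes: "Analytes will not be included in the analyses if more than half of the measurements in a treatment group are below the limit of detection".

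SAP section 11 lists three PD samples per patient. One is pre-dose ("Vitreous Humor sample collected at pre-injection baseline by vitreous tap"); the other two, vitreous and aqueous, are taken at surgery and so are post-dose. SAP 11 neither repeats nor replaces the exclusion rule and leaves the PD analysis to the sponsor. SAP section 15 records no change to the planned analysis. The SAP's 75% rule for values below the limit of quantification applies to ONL1204 concentrations in plasma and vitreous, not to cytokines.

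Protocol 1.3.3 gives the purpose of the samples: "potential identification of a biomarker for proof of principle of target engagement". Protocol 2.2 says the PK and PD results are to feed into the choice of Phase 2 doses.

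**The concern.** A detectability filter is meant to remove analytes that the assay cannot measure. Here the count can include samples taken after dosing, so the filter partly depends on the effect the PD analysis is looking for. ONL1204 is an inhibitor, and Protocol 1.2.1 describes a preclinical effect on an inflammasome pathway that acts through IL-1β release. A fall below the LOD is therefore a plausible form of response. Nothing in the rule protects an analyte that was detectable before injection or in other cohorts.

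At stake is the target-engagement evidence. An analyte measurable at baseline and undetectable at the higher doses would be informative for Phase 2 dose selection, yet it could be left out of the analyses.

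**Working it through.** **Inputs from the documents.** There are 4 cohorts and 16 patients in total (Protocol 4.1: "Sixteen patients will be enrolled in 4 ascending dose groups"), with 4 patients per cohort (Protocol Study Schematic: "After all 4 patients in a cohort have completed Visit 5"). Each patient gives one pre-dose vitreous, one post-dose vitreous and one post-dose aqueous sample (SAP 11 and the Schedule of Assessments). The plan has no figure to reproduce; on sample size Protocol 9.1.2 says only: "No formal sample size calculation is provided given the pilot nature of this study".

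**Assumptions, not in the documents.** The below-LOD rate is p0 before dosing (0% to 30%) and p1 after dosing (80% for strong suppression). Samples are independent.

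**Trigger counts.** More than half of m samples means at least floor(m/2) + 1:
- (a) one fluid at one visit, here a post-dose one: m = 4, trigger 3
- (b) pre- and post-dose vitreous pooled: m = 8, trigger 5
- (c) all three samples pooled: m = 12, trigger 7

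**Full suppression with all four baselines detectable.** (a) 4 of 4, excluded. (b) 4 of 8, exactly half, kept. (c) 8 of 12, excluded. Under (b), one baseline value below the LOD makes it 5 of 8 and the analyte is excluded. With p0 = 10% the chance of at least one such value is 1 − 0.9⁴ = 0.34.

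**Chance of exclusion in one cohort at p1 = 80%.**
- (a) P(X ≥ 3), X ~ Bin(4, 0.8): 4 × 0.8³ × 0.2 + 0.8⁴ = 0.4096 + 0.4096 = 0.819.
- (b) P(B + V ≥ 5), B ~ Bin(4, p0), V ~ Bin(4, 0.8).
- (c) P(B + W ≥ 7), W ~ Bin(8, 0.8). At p0 = 0: 8 × 0.8⁷ × 0.2 + 0.8⁸ = 0.336 + 0.168 = 0.503.

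| Baseline rate p0 | (a) | (b) | (c) |
|---|---|---|---|
| 0% | 82% | 0% | 50% |
| 10% | 82% | 16% | 61% |
| 20% | 82% | 32% | 70% |
| 30% | 82% | 47% | 78% |

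**Same calculation with no drug effect (p1 = p0).**

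| Rate | (a) | (b) | (c) |
|---|---|---|---|
| 10% | 0.4% | 0.04% | under 0.01% |
| 20% | 2.7% | 1.0% | 0.4% |
| 30% | 8.4% | 5.8% | 3.9% |

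Except in (b) with p0 = 0, suppression raises the chance of exclusion sharply.

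**Scope.** Suppose one cohort's trigger removes the analyte for all, and post-dose rates rise with dose as 10%, 25%, 50% and 75%. On reading (a) the cohort chances are 0.0037, 0.0508, 0.3125 and 0.7383. The analyte is lost with probability 1 − 0.9963 × 0.9492 × 0.6875 × 0.2617 = 0.83. With no effect and a 30% rate everywhere, the figure is 1 − (1 − 0.0837)⁴ = 0.295; that is random loss and not loss through response.

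**Independence.** Post-dose vitreous and aqueous from the same eye are probably correlated. If they always agreed, reading (c) at p0 = 0 would need all four patients below the LOD: 0.8⁴ = 0.41 instead of 0.50.

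**The case against.** The rule has a proper purpose: with 3 of 4 values set at the LOD, a cohort's mean, SD and change from baseline mostly describe the assay. PD is exploratory, SAP section 3 plans no formal testing, and the primary objective rests on safety data. Protocol 9.3.3 allows further exploratory analyses of dose-related measures, and SAP 11 says analyte concentrations will be provided. These points stand and they limit the severity. They do not remove the problem: the further analyses are optional, and a stated exclusion rule governs the planned comparisons.

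A reader might infer that the protocol applies the filter specifically to post-dose results, so that any fully suppressed cytokine is lost. The text does not say that. It leaves visit, fluid and pooling open, and on reading (b) with four detectable baselines the analyte is always kept.

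A reader might also infer that the strongest suppression is removed first. The documents do not support that either. The filter acts on where values end relative to the LOD, not on fold-change. An analyte with a high baseline can fall a long way and stay measurable, while one already near the LOD can trigger the rule after a small fall. No assay limits or baseline levels are given.

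**Conclusion.** The concern holds in a bounded form. The rule does not confine the count to pre-dose samples, so it can exclude a cytokine because the drug lowered it below the LOD, and the SAP does not repair this. The size depends on choices the protocol does not state. At an assumed 80% post-dose below-LOD rate, with independence, exclusion in a cohort of 4 has probability 82% (one fluid and visit), about 50% to 78% (all samples pooled) or 0% to 47% (vitreous pooled), the ranges covering baseline rates of 0% to 30%.

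The direction of the problem follows from the rule's wording and the sample counts; only the percentages rest on assumed rates. Severity is low to moderate, and this is a cheap improvement to an exploratory analysis.

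**What to change.** Replace the exclusion sentence with a rule that does not turn on one cohort's post-dose result:

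- **Vitreous:** exclude an analyte only if more than half of the pre-injection taps, pooled over all cohorts, are below the LOD and more than half of the surgical vitreous samples are below the LOD in every cohort.
- **Aqueous:** exclude only if more than half of the samples are below the LOD in every cohort. The Schedule of Assessments has no baseline aqueous sample.
- **Retained analytes:** report the number below the LOD by cohort, fluid and visit. Where more than half of a cohort's values are censored, use the proportion detectable or rank-based summaries, not means or SDs.

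For vitreous, the pooled-tap condition needs at least 9 of 16 below the LOD. Whatever the drug does, that has probability 2.6% at a 30% baseline rate, which caps the chance of wrongly losing the analyte. The aqueous rule is weaker, because it still uses post-dose data: if all four doses suppressed to 80% below the LOD, exclusion would have probability 0.8192⁴ = 0.45. With the dose gradient above it would be negligible (0.0037 × 0.0508 × 0.3125 × 0.7383 = 0.00004).

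The sampling text should be reconciled at the same time. Protocol 6.4.2 describes the baseline vitreous tap as post-injection and lists a baseline anterior chamber tap, while the Schedule of Assessments and SAP 11 have a pre-injection vitreous tap and aqueous at surgery only.

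Cost: a few sentences, and a few heavily censored analytes staying in exploratory tables. Because the rule is in the protocol, the change must be documented, either in the SAP (section 15 now lists none) or as an amendment, which under Protocol section 12 needs ethics committee approval.

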9.3.4 Demographic and Baseline Characteristics

Demographic information (age, sex, ethnicity, race) will be summarized by treatment arm based on the ITT population.

9.4 Interim Analysis

There are no plans to conduct an interim analysis for this study.

10 ETHICS AND RESPONSIBILITIES

10.1 Good Clinical Practice

The study will be conducted in accordance with the ICH GCP and the appropriate regulatory requirements. The investigator will be thoroughly familiar with the appropriate use of the study drug as described in the protocol and the IB.

10.2 Safety Review Committee

A safety review committee (SRC) comprising of relevant site investigators, the medical monitor, and sponsor representative will oversee safety, sentinel patient clearance, cohort evaluation, and dose escalation for the study. A formal charter will be established to include the rules, meeting frequency, and scope of responsibilities of the SRC for the conduct of the SRC. The respective IRB's will be informed of the outcome of the SRC meetings.

The decision to dose-escalate to the next cohort will include evaluation of potential dose limiting toxicities as detailed in Section 4.2.1 as well as adverse events, clinical laboratory evaluations and ophthalmologic imaging data. Applicable sections of the Common Terminology Criteria for Adverse Events (CTCAE) version 5, 17Nov2017 will be used to grade adverse events.

10.3 Human Research Ethics Committee

The study will be conducted in accordance with applicable regulatory requirement(s) and will adhere to GCP standards. The HREC will review all appropriate study documentation to safeguard the rights, safety, and well-being of the patients. The study will be conducted only at sites where HREC approval has been obtained. The protocol, IB, informed consent form, advertisements (if applicable), written information given to the patients, safety updates, annual progress reports, and any revisions to these documents will be provided to the HREC by the investigator or the sponsor, as allowed by local regulations.

10.4 Informed Consent

After the study has been fully explained, written informed consent will be obtained from the patient before study participation. The method of obtaining and documenting the informed consent and the contents of the consent must comply with the ICH GCP and all applicable regulatory requirements.

10.5 Records Management

The investigator is required to prepare and maintain adequate and accurate case histories designed to record all observations and other data pertinent to the study for each study patient. Study data will be entered into an eCRF by site personnel using a secure, validated, web-based electronic data capture (EDC) application. ONL Therapeutics will have access to all data upon entry in the EDC application.

Study monitors will discuss instances of missing or uninterpretable data with the investigator for resolution. Any changes to study data will be made to the eCRF and documented via an electronic audit trail associated with the affected eCRF.

10.6 Source Documentation

The study sites will be provided with secure access to and training on the EDC application, sufficient to permit site personnel to enter or correct information in the eCRFs for the patients for whom they are responsible.

eCRFs will be completed for each patient. It is the investigator's responsibility to ensure the accuracy, completeness, clarity, and timeliness of the data reported in the patient's eCRF.

The investigator, or designated representative, should complete the eCRF within 5 business days of visit.

10.7 Study Files and Record Retention

The investigator will maintain all study records according to the ICH GCP and applicable regulatory requirement(s). Records will be retained for at least 2 years after the last marketing application approval or 2 years after formal discontinuation of the clinical development of the investigational product or according to applicable regulatory requirement(s). If the investigator withdraws from the responsibility of keeping the study records, custody must be transferred to a person willing to accept the responsibility and ONL Therapeutics must be notified.

11 AUDITING AND MONITORING

Monitoring and auditing procedures developed or approved by ONL Therapeutics will be followed to comply with GCP guidelines.

All information recorded on the eCRFs for this study must be consistent with the patient's source documentation. Study monitors will visit the sites throughout the study to review and confirm that information in the eCRF corresponds with source documents for the patient. They will also assess drug accountability and ensure that the study is being conducted according to pertinent regulatory requirements. The review of all patient data will be performed in a manner that ensures patient confidentiality is maintained.

12 AMENDMENTS

Protocol modifications, except those intended to reduce immediate risk to study patients, may be made only by ONL Therapeutics. A protocol change intended to eliminate an apparent immediate hazard to patients may be implemented immediately, provided the HREC is notified within 5 days.

Any permanent change to the protocol must be handled as a protocol amendment. The written amendment must be submitted to the HREC and the investigator must await approval before implementing the changes. ONL Therapeutics will submit protocol amendments to the appropriate regulatory authorities for approval.

If in the judgment of the HREC, the investigator, and/or ONL Therapeutics, the amendment to the protocol substantially changes the study design and/or increases the

potential risk to the patient and/or has an impact on the patient's involvement as a study participant, the currently approved written informed consent form will require similar modification. In such cases, informed consent will be renewed for patients enrolled in the study before continued participation.

13 STUDY REPORT AND PUBLICATIONS

ONL Therapeutic is responsible for preparing and providing the appropriate regulatory authorities with clinical study reports according to the applicable regulatory requirements.

The publication policy of ONL Therapeutics is discussed in the investigator's Clinical Research Agreement.

